3.3 Sample size

The sample size was estimated with the aim of showing a significant reduction of the composite primary endpoint in the intervention arm compared to the control arm. The significance level was chosen to be 5%, while the power was chosen to be at least $(1-\beta) = 80\%$.

Based on the available literature and own experience at the study sites, we compared various realistic scenarios of what ratio of participants would reach the primary endpoint in each study arm (see Table 1).

Table 1: Sample size for different scenarios with 80% power and $\alpha = 0.05$.

Difference ^a	PInt	PC	n (per arm)
20%			
	0.25	0.45	89
	0.20	0.40	82
	0.15	0.35	73
15%			
	0.25	0.40	152
	0.20	0.35	138
	0.15	0.30	121

^a Reduction of the event rate for the treatment group compared to the control group. PInt: Probability of event in the intervention group; PC: Probability of event in the control group.

As our hypothesis for the sample size calculation, we selected the scenario in which 20% vs 35% of participants reach the primary endpoint in the intervention vs the control arm. Using a Pearson's chi-squared test with a significance level of 5% and a power of 80%, a required sample size of calculated (see Table 1).

Participants prematurely leaving the study will not be replaced.

3.4 Framework

This is a superiority trial.

3.5 Statistical interim analyses and stopping guidance

One formal interim analysis is planned. The cut-off for this interim analysis is planned when 138 participants (50% of the intended sample size) have completed the 9-month study visit and/or reached the primary endpoint. The same analysis as planned for the final analysis will be performed for the composite primary endpoint. However, only stratification variables will be included in the analysis and no sensitivity analyses will be done.

The trial may be concluded early for success if a significant difference between the two trial arms for the composite primary endpoint is achieved at the time of the interim analysis. We will use the conservative Haybittle-Peto stopping level of $p=0.001$ [3].

In addition, premature stopping due to futility will be considered if obtaining a difference of ≥ 10 percentage points between the study arms is unlikely to be demonstrated. The trial will be stopped for inefficacy if the odds ratio is greater than 1 and the two-sided 95% confidence interval does not contain the alternative hypothesis (i.e., odds ratio of 0.57) [4].

The interim analysis will be performed by an external independent statistician at an external data analysis center, who will not be involved in the study conduct and will be blinded for the treatment allocation. The results will be reviewed by a Data Safety Monitoring Board, who will issue a recommendation to continue or stop the trial to the Steering Committee. The Steering Committee will vote on and thereby determine the continuation or termination of the trial. In the event of a tie, the Sponsor/Chief Investigator will cast the deciding vote.

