3.1 Trial design

Full details of the trial are available in the current version (V 1.4) of the trial protocol as well as in summary version in the published protocol[2].

GIVE MOVE is an open-label, two-arm, multi-center, superiority randomised clinical trial conducted in Lesotho and Tanzania. Enrollment takes place in 10 sites (6 in Lesotho, 4 in Tanzania). Participants will be randomized in a 1:1 ratio to the intervention or the control arm. In the intervention arm, GRT (Sanger sequencing) will be performed. Based on the GRT and clinical information, an international expert committee issues a recommendation on the ART regimen and management. Taking this recommendation, the GRT as well as availability of drug formulations into account, the health care provider in charge of the

¹ WHO stage 4 events that are excluded: lymph node tuberculosis, stunting, oral or genital herpes simplex infection and oesophageal candidiasis

participant then takes the final decision on the composition of the ART regimen. Participants in the control arm will be managed according to the standard of care. Onward treatment will be informed by the follow-up VL in line with standard care and without performing resistance testing. The composite primary endpoint will be assessed 9 months (window: 32-44 weeks) after randomization (see Figure 1).

Although participants and treating healthcare professionals will not be blinded, laboratory technologists measuring the viral load (a key component of the primary and some secondary endpoints) will be blinded, as will the endpoint committee assessing if hospitalizations and potential WHO stage 4 events constitute an endpoint.

[figure not shown]

Figure 1: Overview of GIVE MOVE treatment algorithm and study visits. The decision follow-up visit is not shown. GRT: genotypic resistance testing; VL: viral load.

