4.1 Confidence intervals and p-values

Statistical tests and confidence intervals will be two-sided. All estimates will be presented with 95% confidence intervals. P-values will be presented where appropriate. No adjustments will be made for multiple testing; interpretations will be based on the strength of evidence of effect size and consistency of results for related outcomes.

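### The futility rule tests against an odds ratio of 0.57, which is the design risk ratio (the design odds ratio is 0.46), and a second, undefined 10-point criterion stands beside it

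*SAP*

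**What the plan says.** SAP section 3.5 plans one interim analysis at 138 participants, half of the intended sample. Its futility paragraph has two sentences.

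- The first lets early stopping be considered "if obtaining a difference of ≥ 10 percentage points between the study arms is unlikely to be demonstrated".
- The second is mandatory in wording: "The trial will be stopped for inefficacy if the odds ratio is greater than 1" and the two-sided 95% interval "does not contain the alternative hypothesis (i.e., odds ratio of 0.57").

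Section 3.3 fixes the alternative: "we selected the scenario in which 20% vs 35% of participants reach the primary endpoint", intervention vs control, "with a significance level of 5% and a power of 80"%. Section 4.1 makes tests and intervals two-sided, and section 3.1 sets 1:1 allocation. Section 3.5 does not say that the second futility sentence implements the first, or which one governs.

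**The concern.** A futility rule that excludes the alternative must name the alternative on the scale of the interval. Here the interval is for an odds ratio, but the number is what 20% vs 35% gives as a ratio of risks. The board would then be testing against a weaker effect than the one the trial was sized for.

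The 10-point sentence adds another target, on the risk-difference scale and without a calculable threshold. An interim result can therefore prompt consideration of stopping while the mandatory rule is not met. The Data Safety Monitoring Board recommends and the Steering Committee votes, so the meaning of the sentence could end up being argued after the interim results are known.

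**Working it through.** **Inputs.** 20% vs 35%, 5% significance and 80% power (SAP 3.3); two-sided (4.1); 1:1 (3.1); interim at 138 in total, so about 69 per arm, and final 138 per arm (3.5 and Table 1).

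**The plan's own figure.** n = [1.96·√(2·0.275·0.725) + 0.8416·√(0.20·0.80 + 0.35·0.65)]² / 0.15² = 137.9, so 138 per arm. This agrees with Table 1.

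**The alternative on each scale**

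- Odds ratio, 20% vs 35%: (0.20/0.80)/(0.35/0.65) = 0.250/0.538 = 0.464.
- Risk ratio: 0.20/0.35 = 0.571.
- An odds ratio of 0.57 with 35% control: odds 0.57 × 0.538 = 0.307, risk 0.307/1.307 = 23.5%, so 11.5 points.
- Ten points, 25% vs 35%: (0.25/0.75)/0.538 = 0.62.
- The six rows of Table 1 have odds ratios 0.41, 0.38, 0.33, 0.50, 0.46 and 0.41. None is 0.57. Only the selected row has a risk ratio of 0.57.

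**Does the label change a decision?** Unadjusted Wald intervals, control 24/69:

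- Intervention 25/69: OR = (25×45)/(44×24) = 1.07; SE of log OR = √(1/25+1/44+1/24+1/45) = 0.356; interval 0.53 to 2.14. It contains 0.57 (continue) and excludes 0.464 (stop).
- 26/69: OR 1.13 (0.57 to 2.27, lower limit 0.566). Same split.
- 27/69: OR 1.21 (0.60 to 2.41). Stops against either value.

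**The 10-point criterion, 22 vs 24 events.** The interim difference is 2/69 = 0.029. A final observed difference of 0.10 needs 0.171 in the second half.

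- Current trend: (0.171 − 0.029)/0.080 = 1.77, probability 3.8%.
- Remaining data at 20% vs 35%: (0.171 − 0.150)/0.075 = 0.28, probability 39%.

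The odds ratio is 0.88 (0.43 to 1.78), so the mandatory rule is not met.

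**How often.** Exact binomial enumeration at 69 per arm, with *unlikely* taken as a probability below 10% to 30% (an assumption, as the SAP gives none):

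| | 10-point, current trend | 10-point, rest at 20% vs 35% | OR rule, 0.57 |
|---|---|---|---|
| Triggers, truth 20% vs 35% | 9-17% | 0.4-2.9% | 0.6% |
| Triggers, truth 35% in both | 73-84% | 27-54% | 34% |
| Differs from OR rule, 35% in both | 40-50% | 7-20% | – |

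In most settings the 10-point criterion is the wider of the two. With a 10% cut-off and the design-effect projection the order reverses: 27 vs 24 events meets the odds-ratio rule, while the 10-point probability is 10.6%.

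**Effect of correcting the threshold**, same enumeration:

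| Rule | Truth 20% vs 35% | Truth 35% in both |
|---|---|---|
| OR > 1, interval excludes 0.57 | 0.6% | 34% |
| OR > 1, interval excludes 0.464 | 1.8% | 46% |
| RR > 1, interval excludes 0.571 | 1.7% | 46% |
| OR > 1 alone | 1.8% | 46% |

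**The case against.** A reader might infer that the same interim data can order both stopping and continuing. The text does not support that. The first sentence only allows stopping to be considered, and the second never orders continuation when it is not met. A discretionary trigger beside a hard one is compatible, and the first sentence may simply state the aim. This stands, and it limits the point to undefined guidance with no stated precedence.

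The 10 points may also be a result to be seen in the final data, not a rival true effect. The smallest significant observed difference at 138 per arm is about 1.96·√(2p(1−p)/138), or 10.5 to 10.8 points for p from 0.275 to 0.30. Ten points lies close to that. On this reading it does not compete with the 15-point design effect, and the trial's power against a true 10-point effect is beside the point.

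A reader might further infer a large loss of power. That depends on the projection. On the current trend, stopping on the 10-point sentence would lower power from 80% to 73-78%; under the design effect it would cost at most 0.4 points. Even the 3.8% in the example becomes 10.5% when the uncertainty of the interim rates is allowed for.

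The protocol may give a cut-off, so its absence here is weaker evidence than the label. None of these arguments rescues 0.57 as the odds ratio of the alternative. If a weaker effect was intended, the SAP does not say so and calls it the alternative hypothesis.

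**Conclusion.** The 0.57 is wrong as written. It is the risk ratio of 20% vs 35% used as an odds ratio, whatever *unlikely* means. The consequence is confined to a narrow band of interim results, such as 25 or 26 vs 24 events, where the intervention is slightly worse than control. As written the rule stops less often than one built on the design alternative: 34% against 46% of trials with no effect.

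The 10-point criterion is under-specified. Its trigger rate under the planned effect can lie anywhere from 0.4% to 17%, and the choice of projection matters more than the cut-off. The figures of 9-17% and 40-50% belong to the current-trend reading only and should not be cited alone.

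All rates assume 69 per arm, a 35% control rate, unadjusted intervals and a normal approximation for the second half. The planned model adjusts for the stratification factors, so exact boundaries will shift slightly.

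**What to change.** Keep one operative futility rule in SAP section 3.5.

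1. Delete the 10-point sentence, or say that it is only the aim and that the confidence-interval rule governs.
2. Correct the threshold to the design odds ratio, 0.46, or express the rule as a risk ratio with 0.57. The second choice needs a stated method for the risk ratio, since section 6.2 reports odds ratios and risk differences.
3. State the consequence. With either correction the interval clause adds almost nothing to the condition that the estimate exceeds 1. Stopping becomes more frequent, as shown in the second table. The cost in power is small: by the same enumeration, from 80.3% to 80.1%.
4. Alternatively, replace both sentences with one conditional-power limit computed under 20% vs 35%, with the limit given and a statement of whether it is binding.

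The edit is to the SAP text, and to the protocol if it carries the same wording. Sample size and data collection do not change. The operating characteristics do, so the change should be made before interim data are seen.

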6.2 Analysis methods

Continuous variables will be inspected using histograms: 1) to assess for outliers which may be queried for accuracy, and 2) to assess whether appropriate transformations are required for modeling.

Endpoints will be summarized using medians and interquartile ranges for continuous variables and numbers and percentages for categorical variables, by randomized group. Percentages will be reported to one decimal place.

We will present numbers and proportions of participants achieving each of the four components of the composite endpoint separately. Those with missing VL results will be handled as

described in section 6.1 and reasons for missing VL results will be provided.

For the analysis of the primary outcome, we will use a logistic regression model adjusted for the randomization stratification factors (country, age, and ART regimen; see section 3.2) and relevant baseline characteristics found to be unbalanced between intervention and control clusters (as described above in section 5.5). Results will be reported as odds ratios with 95% confidence intervals. Further, we will estimate the absolute risk difference, with 95% confidence intervals estimated using the delta method [7].

Sensitivity analyses

In a first sensitivity analysis for the primary outcome, we will analyze the PP set (see section 4.2). Protocol violations and deviations will be described. We will summarize the data (numbers and proportions of participants included in this analysis, and meeting the primary endpoint), and fit logistic regression models as for the main primary outcome analysis.

As a second sensitivity analysis of the primary outcome, we will also consider an additional two definitions of viral suppression - <400 and <1000 copies/mL.

Subgroup analysis

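### The inefficacy rule in SAP section 3.5 labels 0.57 an odds ratio, but the planned alternative (20% vs 35%) has an odds ratio of 0.46; 0.57 is its risk ratio

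*SAP*

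**What the plan says.** - **The alternative.** SAP section 3.3: "we selected the scenario in which 20% vs 35% of participants reach the primary endpoint in the intervention vs the control arm". Table 1 gives 138 per arm for this row, at 5% significance and 80% power.
- **The inefficacy rule.** SAP section 3.5 has two conditions at the interim: the odds ratio exceeds 1, and "the two-sided 95% confidence interval does not contain the alternative hypothesis (i.e., odds ratio of 0.57"). The interim falls at 138 participants, half the intended sample.
- **The scale of the interim estimate.** Section 3.5: "The same analysis as planned for the final analysis will be performed for the composite primary endpoint", with the limits that "only stratification variables will be included in the analysis and no sensitivity analyses will be done". In section 6.2 the primary analysis is a logistic regression: "Results will be reported as odds ratios with 95% confidence intervals". The only other effect measure is on the difference scale: "we will estimate the absolute risk difference, with 95% confidence intervals estimated using the delta method". No risk ratio is planned.
- **Who decides.** Section 3.5: "The Steering Committee will vote on and thereby determine the continuation or termination of the trial", after a recommendation from the Data Safety Monitoring Board.

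**The concern.** The rule gives its threshold twice, as the alternative hypothesis and as the number 0.57, and the two disagree. Someone applying the number and someone applying the definition can reach opposite answers from the same interim data.

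The direction is fixed. Once the observed odds ratio exceeds 1, the interval can exclude a value below 1 only if its lower limit lies above that value. A higher threshold is harder to clear, so the printed 0.57 makes the rule harder to meet. What is at stake is the chance that an ineffective or harmful intervention is flagged at half the sample.

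**Working it through.** **Inputs.** Event probabilities 0.20 and 0.35, two-sided 5% significance and 80% power (sections 3.3 and 4.1). Interim of 138 participants at 1:1 (sections 3.1 and 3.5), taken as 69 per arm.

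**1. Confirm the alternative by reproducing Table 1.** Pearson chi-squared with pooled variance and no continuity correction:

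n = [1.960·√(2·0.275·0.725) + 0.842·√(0.20·0.80 + 0.35·0.65)]² / 0.15² = (1.2377 + 0.5239)² / 0.0225 = 137.9, so 138 per arm.

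All six rows of Table 1 reproduce the same way, so 20% versus 35% is the alternative behind the sample size.

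**2. Put it on both ratio scales.**

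- Odds ratio = (0.20/0.80)/(0.35/0.65) = 0.2500/0.5385 = 0.464
- Risk ratio = 0.20/0.35 = 0.571

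**3. Look for another source of 0.57.**

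| Intervention vs control (Table 1) | Odds ratio | Risk ratio |
|---|---|---|
| 25% vs 45% | 0.407 | 0.556 |
| 20% vs 40% | 0.375 | 0.500 |
| 15% vs 35% | 0.328 | 0.429 |
| 25% vs 40% | 0.500 | 0.625 |
| **20% vs 35%** | **0.464** | **0.571** |
| 15% vs 30% | 0.412 | 0.500 |

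No row has an odds ratio of 0.57, and only the selected row has that risk ratio. Over all 15-point reductions the largest odds ratio is (0.425/0.575)² = 0.546, at a control rate of 57.5%.

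**4. See why the value matters at this sample size.** With 35% events in both arms, the standard error of the log odds ratio is √[2/(69·0.35·0.65)] = 0.357. At an observed odds ratio of 1, the lower 95% limit is about exp(−1.96·0.357) = 0.50. That is already above 0.464 but below 0.57. Under 0.464, any odds ratio above 1 meets the rule. Under 0.57, the observed odds ratio must exceed about 0.57·exp(1.96·0.357) = 1.15.

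In counts, with 24/69 control events:

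| Intervention events | Odds ratio (95% CI) | Excludes 0.464 | Excludes 0.57 |
|---|---|---|---|
| 25/69 | 1.07 (0.530–2.14) | yes | no |
| 26/69 | 1.13 (0.566–2.27) | yes | no |
| 27/69 | 1.21 (0.603–2.41) | yes | yes |

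**5. Chance of meeting the rule.** Exact enumeration of two binomials of 69, unadjusted Wald interval:

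| True rates (intervention/control) | Threshold 0.57 | Threshold 0.464 | Odds ratio > 1 alone |
|---|---|---|---|
| 35%/35% | 33.5% | 46.5% | 46.5% |
| 40%/35% | 58.5% | 69.9% | 69.9% |
| 25%/35% | 4.0% | 8.3% | 8.3% |
| 20%/35% | 0.65% | 1.80% | 1.81% |

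The planned interim model is adjusted. Simulation of a logistic model with country, age and regimen (12 equal strata and a log odds ratio per factor of 0 to 0.7, both assumed) gives 30–33% versus 48–49% at 35%/35%, 55–57% versus 72% at 40%/35%, and 3–4% versus 8–10% at 25%/35%.

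**6. Effect on the whole design.** Simulation of 1,000,000 trials, with efficacy at p < 0.001 at the interim and p < 0.05 at 138 per arm, 0.57 versus 0.464: power 80.3% versus 80.1% at 20%/35%, and 44.3% versus 44.1% at 25%/35%. False positives in favour of the intervention at 35%/35% are 2.55% versus 2.53%.

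**The case against.** **The consequence is limited.** The misprint leaves the efficacy boundary and the final analysis untouched, and it errs toward continuing. A board and a committee stand between the rule and any stop. This stands and limits the severity, but the number is still a pre-specified stopping threshold.

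**0.57 could be a deliberate, weaker target.** Section 3.5 also mentions a difference of at least 10 percentage points. However, 10 points below 35% is an odds ratio of (0.25/0.75)/(0.35/0.65) = 0.62. A 10-point reduction has an odds ratio of 0.57 only at control rates of 28.6% or 81.4%, neither of which is in the SAP. The text also equates 0.57 with the alternative hypothesis. A mislabelled risk ratio is the likeliest cause, though the SAP does not say so.

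**The interim odds ratio is conditional on the strata, whereas 0.464 is marginal.** True, but the conditional value for the same risks lies further from 0.57: about 0.43 to 0.44 under the assumed log odds ratio of 0.7 per factor.

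**Correcting to 0.46 leaves the interval condition almost idle.** This also stands. At event rates of about 25% to 35% the rule becomes little more than odds ratio above 1. The condition removes about 3 points at 20% in both arms (45.8% to 42.4%) and about 9 at 15% (45.2% to 36.0%). A sponsor could prefer a stricter threshold, but should then choose and name it as such.

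**Conclusion.** The concern holds and should be fixed. The odds ratio of the selected alternative is 0.46, and 0.57 is its risk ratio. As printed, the rule is met about 13 percentage points less often than its definition when both arms have 35% events, and about 11 points less often at 40% versus 35%. Power changes by about 0.2 points and type I error is not inflated.

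The contradiction follows from the SAP's own figures. The probabilities assume 69 per arm and an unadjusted Wald interval. The adjusted-model figures also rest on assumed strata and covariate effects and are illustrative; they show a similar or larger gap.

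**What to change.** Before the interim, adopt one of the following. The choice is the sponsor's.

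- **(a) Correct the number.** State an odds ratio of 0.46 (20% versus 35%). Cost: one number and a clause, which should acknowledge that the interval condition then adds almost nothing to an odds ratio above 1 at event rates of about 25% to 35%.
- **(b) Correct the label.** Call 0.57 a risk ratio, put the interval on the risk-ratio scale and add a method for it, since section 6.2 has none. At a 35% control rate this performs almost as (a) does (46.4% at 35%/35%, 8.3% at 25%/35%). At lower rates it is met less often (37% versus 42% at 20%/20%).
- **(c) Keep a weaker effect on purpose.** Stop calling it the alternative hypothesis, and give its event rates and odds ratio. Cost: one sentence.

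Under (a) or (b) power falls by about 0.2 percentage points at 20% versus 35% and at 25% versus 35%. The chance of meeting the rule at a true 25% versus 35% rises from about 4% to 8%.

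In each case, add a clause on how the 10-point sentence relates to the threshold. That sentence is not itself an error, but at a 35% control rate it corresponds to an odds ratio of 0.62.

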3.6 Timing of final analysis

Outcomes will be analysed after the last participant has completed the study.

3.7 Timing of outcome assessments

Table 2 shows the timing of outcome assessments, the permitted ranges according to the protocol, and the ranges that will be used for analysis. The protocol provides all times in months and weeks. The lower and upper limits of the analysis windows correspond to the lower and upper protocol-defined limit, respectively.

If more than one value of the viral load outcome is collected during the analysis window, the first one in the analysis window will be used.

Table 2. Follow-up and permitted windows for endpoints.

Follow-up, months	Follow-up, weeks	Range according to the protocol, weeks	Analysis window, days
3	12	10 – 14	≥ 70 and < 98
6	24	20 – 28	≥ 140 and < 196
9	36	32 – 44	≥ 224 and < 308
9	44	Up until study completion*	< 308

4. Statistical principles

